3.1.1.1. Hypoglycemia Monitoring and Reporting

Hypoglycemia AEs will be recorded in the AE Case Report Form (CRF) with details of the event captured on the Hypoglycemic Event Details CRF. Details of when these will be recorded are given in the protocol (Section 8.2.4.2).

For programming purposes, the hypoglycemic AE categories are based on the following:

- **Severe Hypoglycemia:** Severe is checked in the severity criteria of the CRF. This assessment will be made by the PI based on the protocol definition.
- **Documented Symptomatic Hypoglycemia:** If (2 – Did the participant have symptoms of hypoglycemia?) Yes and (3 – Was the blood glucose measured?) Yes and result

<70 mg/dL (or <3.9 mmol/L) on the CRF, but hypoglycemia is not classified as severe.

- Asymptomatic Hypoglycemia: If (2) No and (3) Yes and result <70 mg/dL (or <3.9 mmol/L) on the CRF, but hypoglycemia is not classified as severe.
- Probable Symptomatic Hypoglycemia: If (2) Yes and (3) No and (3a – If blood glucose was not measured, did symptoms resolve when treated with carbohydrate or glucagon?) Yes on the CRF, but hypoglycemia is not classified as severe.

3.1.2. Safety Laboratory Tests

Safety laboratory tests (hematology, chemistry, urine testing and other clinical laboratory tests) will be performed as described in the protocol.

To determine if there are any clinically significant laboratory abnormalities, the safety tests will be assessed against the criteria specified in the sponsor reporting standards. The assessment will take into account whether each participant's baseline test result is within or outside the laboratory reference range for the particular laboratory parameter.

Baseline for all laboratory measurements will be defined as the result assessed on Day -1.

3.1.3. Vital Signs

Vital sign measurements (systolic blood pressure, diastolic blood pressure and pulse rate) will be taken as detailed in the Schedule of Activities given in the protocol. The average of the triplicate measurements collected at each appropriate assessment time will be calculated for each vital sign parameter.

Baseline will be defined as the result assessed on Day -1 per SoA, where "result" refers to the average of a triplicate measurement.

Changes from baseline for supine systolic and diastolic blood pressure and pulse rate will be calculated for each post baseline measurement.

The time-matched double difference in supine blood pressures and pulse rate measurements is calculated in the following steps: (1) subtract the average of the triplicate predose values on Day 1 from all postdose values; (2) subtract the value at 0 hours on Day -1 from all other values on Day -1; (3) take the difference between the adjusted postdose value in (1) and its time-matched value in (2).

3.1.4. Electrocardiograms

Standard 12-lead ECG (including heart rate, QT, QTcF, PR and QRS interval) will be obtained at times detailed in the Schedule of Activities given in the protocol. The average of the triplicate readings collected at each appropriate assessment time will be calculated for each ECG parameter.

ECG endpoints include heart rate, QT interval, PR interval and QRS interval. If not supplied QTcF will be derived using Fridericia's heart rate correction formula:
 $QTcF = QT / (RR)^{(1/3)}$, where $RR = 60/HR$ (if RR is not provided).

Baseline will be defined as the result assessed on Day -1 per SoA, where "result" refers to the average of a triplicate measurement.

Change from baseline for heart rate, QT, QTcF, PR and QRS interval will be calculated for each post baseline measurement.

The time-matched double difference in heart rate, QT, QTcF, PR and QRS measures is calculated in the following steps: (1) subtract the average of the triplicate predose values on Day 1 from all postdose values; (2) subtract the value at 0 hours on Day -1 from all other values on Day -1; (3) take the difference between the adjusted postdose value in (1) and its time-matched value in (2)

3.2. Secondary Endpoint(s)

Blood samples for PK analysis of PF-07081532 will be taken according to the Schedule of Activities given in the protocol.

Plasma PF-07081532 PK parameters following single or multiple dose administration of PF-07081532 will be derived using standard noncompartmental methods, as data permit, for each treatment and day (as appropriate), from the concentration time profiles as follows:

Table 2. PF-07081532 PK Parameters

Parameter	Analysis Scale	PF-07081532	Assessment Day
AUC ₂₄	Ln	D	D1 and D42
AUC ₂₄ (dn)	Ln	D	D1 and D42
C _{max}	Ln	D	D1 and D42
C _{max} (dn)	Ln	D	D1 and D42
T _{max}	R	D	D1 and D42
t _{1/2} *	R	D	D42
PTR	Ln	D	D42
R _{ac}	Ln	D	D42
C _{av}	Ln	D	D42
C _{min}	Ln	D	D42
R _{ac,Cmax}	Ln	D	D42
CL/F*	Ln	D	D42
V _Z /F*	Ln	D	D42
AUC _{inf} *	Ln	D	D42
AUC _{last}	Ln	D	D42

Key: D=displayed with descriptive statistics, Ln=natural-log transformed, R=raw (untransformed), *=if data permits.

3.3. Other Endpoint(s)

3.3.1. Change from Baseline in Insulin, Glucagon and C-Peptide AUC₀₋₄

Baseline for Insulin, Glucagon and C-Peptide AUC₀₋₄ following MMTT will be defined as the AUC₀₋₄ assessed on Day -1.

Change from baseline, percent change from baseline and relative change from baseline at the end of the study (ie Day 42 for Insulin, Glucagon and C-Peptide AUC₀₋₄) as specified in the schedule of activities will be calculated.

Note: Relative Change from Baseline = Post-dose timepoint Value / Baseline Value

3.3.2. Change from Baseline in Fasting Plasma Glucose, Fasting Plasma Insulin and HOMA-IR

The change from baseline to all post-dose timepoints as specified in the schedule of activities will be calculated.

Remark: Where triplicate fasting plasma insulin (FPI) are assessed, the average of the three measurements will be calculated to be reported at each timepoint and used to derive HOMA-IR. *When three assessments are performed at baseline, FPI baseline will be the average of the three values.*

3.3.3. Change from Baseline in HbA1c

Baseline for HbA1c will be defined as the Day -1. The change from baseline to all post-dose timepoints as specified in the schedule of activities will be calculated.

3.3.4. Change from Baseline in TSH

Baseline for TSH will be defined as the Day -1, 0H time point. The change from baseline to all post-dose timepoints as specified in the schedule of activities will be calculated.

3.3.5. Change from Baseline in FreeT4, Calcitonin, Amylase, Lipase, and Lipids

Baseline for freeT4, calcitonin, amylase, lipase, and lipids will be defined as the Day -1, 0H time point. The change from baseline to all post-dose timepoints as specified in the schedule of activities will be calculated.

3.3.6. Change from Baseline in Body Weight

Baseline for body weight will be defined as the pre-dose measure on Day 1. The change from baseline and percent change from baseline to all post-dose timepoints as specified in the schedule of activities will be calculated.

3.3.7. Baseline Variables

Baseline measures will be included as a covariate in all applicable statistical.

3.4. Other Safety Endpoints

3.4.1.1. Adverse events of interest

The TEAEs of interest for additional reporting are: nausea, vomiting and diarrhoea (as defined based on preferred term). Based on emerging blinded data reviews, other AEs of interest may be added to this list, which would be documented with a SAP amendment or documented in the changes to planned analysis section in the CSR.

4. ANALYSIS SETS (POPULATIONS FOR ANALYSIS)

Data for all participants will be assessed to determine if participants meet the criteria for inclusion in each analysis population prior to unblinding and releasing the database and classifications will be documented per standard operating procedures.

Participant Analysis Set	Description
Enrolled/Randomly assigned to study intervention	"Enrolled" means a participant's, or their legally authorized representative's, agreement to participate in a clinical study following completion of the informed consent process and screening. Potential participants who are screened for the purpose of determining eligibility for the study, but do not participate in the study, are not considered enrolled, unless otherwise specified by the protocol. A participant will be considered enrolled if the informed consent is not withdrawn prior to participating in any study activity after screening.

Participant Analysis Set	Description
Full Analysis Set	All participants randomly assigned to study intervention and who take at least 1 dose of study intervention.
Safety Analysis Set	All participants randomly assigned to study intervention and who take at least 1 dose of study intervention. Participants will be analyzed according to the product they actually received.
PK Concentration Set	The PK concentration population is defined as all randomized participants who received at least 1 dose of PF-07081532 and in whom at least 1 plasma concentration value is reported.
PK Parameter Set	The PK parameter population is defined as all randomized participants that received at least 1 dose of PF-07081532 and have at least 1 of the PK parameters of interest calculated.
PD population Set	The PD population set is defined as all randomized participants that received at least 1 dose of PF-07081532 and have at least 1 of the PD parameters of interest calculated.

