### 4.2.4. Endpoints

Clinical safety laboratory tests, thorough assessments of vital signs and 12-lead ECGs, physical examinations, and AE monitoring will provide essential data to evaluate the safety and tolerability of PF-07081532. To supplement standard clinical safety laboratory tests, calcitonin, amylase, lipase, TSH, T4 and lipid panel will be assessed based on the study population and guided by data available on marketed GLP-1R agonists. In addition, TBA will be assessed, based on non-adverse findings in the nonclinical studies with PF-07081532 (see [Section 2.2.2](#) and the IB).

While GLP-1R agonists typically are not associated with hypoglycemia unless co-administered with anti-diabetic agents that can cause hypoglycemia (such as insulin or sulfonylureas), blood glucose concentrations will be monitored throughout the study via a glucometer at least once daily (pre-breakfast), and careful monitoring of symptomatic hypoglycemic AEs will be performed.

In an effort to reduce variability and better quantify any potential changes in heart rate and BP during the study, all measurements of ECG and vital signs (pulse and BP) will be collected in triplicate (except as noted in the [SoA](#)) and the mean values will be used for analysis at each time point.

The effect of PF-07081532 on glucose response in participants with T2DM will be evaluated by determining the change from baseline in MDG. Since MDG is the time-averaged response over a day, it is expected that this glycemic parameter will be predictive of longer term glycemic control. The effect of PF-07081532 on body weight, FPG and other glycemic markers including insulin, C-peptide, HbA1c, and glucagon will also be assessed. FPG and FPI levels will be assessed and used to calculate HOMA-IR. In order to reduce variability in FPI for HOMA-IR calculation, triplicate measurements will be collected as indicated in the [SoA](#) and [Section 8.9.2](#). In an effort to reduce variability, minimize any potential effect of placebo or CRU confinement and better quantify any potential changes to these parameters, the participants will be admitted to the CRU on Day -7 in order to monitor compliance with background metformin and recommended diet.

Baseline (Day -1) assessments with time-matched procedures will permit within participant comparisons, as appropriate. In addition, placebo-adjusted (between participant) comparisons of dose-response will also be conducted.

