## 6. STUDY INTERVENTION(S) AND CONCOMITANT THERAPY

Study intervention is defined as any investigational intervention(s), marketed product(s), placebo, medical device(s), or study procedure(s) intended to be administered to a study participant according to the study protocol.

For the purposes of this protocol, the term investigational product may be used synonymously with study intervention.

For the purposes of this protocol, study intervention refers to PF-07081532 or matching placebo.

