6. ANALYSES AND SUMMARIES

Data collected before baseline will only be listed , unless otherwise stated.

In case of additional cohorts with non-diabetic participants with obesity, for all relevant analyses, the placebo arm will be presented as two separate treatment groups for the T2DM participants and non-diabetic participants with obesity.

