6.4. Other Endpoint(s)

6.4.1. Change from Baseline in Insulin, Glucagon and C-Peptide AUC₀₋₄

- Estimand strategy: Not applicable
- Analysis set: Pharmacodynamic Population Set
- The natural log-transformed of the relative change from baseline at the end of the study will be included in an ANCOVA model, as described in [Section 5.2.5](#), for each measure separately. The adjusted geometric LSMMeans and adjusted geometric LSMeans differences to placebo (with 90% confidence intervals) will be calculated and plotted.

Absolute values and percent change from baseline will be summarized descriptively by treatment and day as described in [Section 5.2.1](#).

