6.4.2. Change from Baseline in Fasting Plasma Glucose, Fasting Plasma Insulin and HOMA-IR

- Estimand strategy: Not applicable
- Analysis set: Pharmacodynamic Population Set

Absolute values and change from baseline will be summarized descriptively by treatment and timepoint (when applicable) as described in [Section 5.2.1](#).

The change from baseline over time for FPG will be included in an MMRM model as described in [Section 5.2.3](#). The LSMMeans and LSMeans differences to placebo (with 90% confidence intervals) will also be plotted.

The change from baseline over time for FPI and HOMA-IR will be included in an ANCOVA model, as described in [Section 5.2.4](#), for each measure separately. The LSMeans and LSMean differences to placebo (with 90% confidence intervals) will also be plotted.

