6.4.3. Change from Baseline in HbA1c

- Estimand strategy: Not applicable
- Analysis set: Pharmacodynamic Population Set

Absolute values and change from baseline will be summarized descriptively by treatment and timepoint as described in [Section 5.2.2](#)

The change from baseline over time will be included in an MMRM model as described in [Section 5.2.3](#). The LSMeans and LSMean differences to placebo for each timepoint (with 90% confidence intervals) will be plotted.

6.4.4. 4- β -hydroxycholesterol/Cholesterol Ratio

The percent change from baseline to all post-dose timepoints as specified in the SoA will be calculated.

- Estimand strategy: Not applicable
- Analysis set: PD Population Set

Absolute values, and percent change from baseline will be summarized descriptively by treatment and day as per [Section 5.2.1](#).

The percent change from baseline over time will be analyzed with an ANCOVA model as described in [Section 5.2.5](#). The LSMeans and LSMean differences to placebo (with 90% confidence intervals) will be plotted. Results of this analysis may be not included in the CSR.

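### The PD population set admits only participants dosed with PF-07081532, so the placebo differences required in SAP 6.4.1 to 6.4.4 cannot be estimated as written

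*SAP*

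**What the plan says.** - **Definition of the set.** SAP Section 4 states: "The PD population set is defined as all randomized participants that received at least 1 dose of PF-07081532", and adds that at least one PD parameter of interest must be available. Protocol Table 4 uses the same wording. The two PK sets carry the same dosing condition. The Full Analysis Set and the Safety Analysis Set are worded differently and require at least one dose of study intervention.
- **Meaning of study intervention.** Protocol Section 6: "For the purposes of this protocol, study intervention refers to PF-07081532 or matching placebo". The two terms are therefore not interchangeable.
- **Analyses assigned to the set.** SAP 6.4.1, 6.4.2, 6.4.3 and 6.4.4 each name the PD set. Each then asks for a comparison with placebo:
  - 6.4.1 (insulin, glucagon and C-peptide AUC0-4): "adjusted geometric LSMeans differences to placebo (with 90% confidence intervals) will be calculated and plotted".
  - 6.4.2 (FPG): "The LSMMeans and LSMeans differences to placebo (with 90% confidence intervals) will also be plotted". An equivalent sentence covers FPI and HOMA-IR.
  - 6.4.3 (HbA1c): "The LSMeans and LSMean differences to placebo for each timepoint (with 90% confidence intervals) will be plotted".
  - 6.4.4 (4-beta-hydroxycholesterol/cholesterol ratio): "LSMean differences to placebo (with 90% confidence intervals) will be plotted. Results of this analysis may be not included in the CSR".
- **Intent.** Protocol 4.2.4 says that "placebo-adjusted (between participant) comparisons of dose-response will also be conducted". If obesity cohorts are added, the introduction to SAP Section 6 says that "the placebo arm will be presented as two separate treatment groups for the T2DM participants and non-diabetic participants with obesity".

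**The concern.** The dosing condition suits the PK sets, because protocol 9.3.3 says placebo samples are not routinely assayed for drug. It does not suit PD. The footnotes to protocol Table 2 restrict PD sampling by diabetes status and not by treatment arm, so placebo participants give PD samples and then belong to no set on which those samples are analysed.

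Read literally, the treatment factor in the ANCOVA and MMRM models has no placebo level. No difference to placebo can be produced, and the descriptive PD summaries on this set have no placebo column. SAP Section 4 also requires each participant to be classified against the set criteria, and the classification documented, before unblinding and database release. The analyst must then either leave SAP 6.4 undelivered or depart from a documented, prespecified rule.

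**Working it through.** **The plan's own figure.** Protocol 9.5 gives about 12 evaluable participants per cohort, chosen empirically, so there is no power calculation to reproduce. The split agrees: 9 + 3 = 12.

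**Step 1. Who is in the set** (three planned cohorts, 9 active and 3 placebo each; protocol 4.1 and SAP 2.3)
- Randomized: 3 × 12 = 36.
- Active, in the PD set: 3 × 9 = 27.
- Placebo, outside the PD set: 3 × 3 = 9, and 9/36 = 25%.
- Across 1 to 6 cohorts, the excluded count runs from 3 of 12 to 18 of 72. It is 25% throughout at the planned allocation.

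**Step 2. Endpoints with a required placebo difference on this set**

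| SAP section | Endpoints | Model | Count |
|---|---|---|---|
| 6.4.1 | Insulin, glucagon, C-peptide AUC0-4 | ANCOVA, log scale | 3 |
| 6.4.2 | FPG | MMRM | 1 |
| 6.4.2 | FPI, HOMA-IR | ANCOVA, raw scale | 2 |
| 6.4.3 | HbA1c | MMRM | 1 |
| 6.4.4 | 4-beta-hydroxycholesterol/cholesterol ratio | ANCOVA | 1 |
| Total | | | 8 |

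**Step 3. Contrasts required.** Assume each cohort is one treatment (stated for PK in protocol 9.3.3, assumed here for PD), all three planned cohorts are T2DM, and there is one post-dose day per endpoint.
- 8 endpoints × 3 treatments = 24 contrasts.
- HbA1c is scheduled on Days 28 and 42 (protocol Table 2). Its second day adds 3, giving 27.

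**Step 4. Estimability.** Take a design matrix with an intercept, indicators for placebo and three active treatments, and baseline. The contrast of active minus placebo is estimable only if adding its row leaves the rank unchanged.
- As written (0 placebo, 9 + 9 + 9 active): 27 rows, rank 4. The placebo column is all zeros and the contrast row raises the rank. Not estimable.
- With placebo included (9 + 9 + 9 + 9): 36 rows, rank 5. The contrast row leaves the rank at 5. Estimable.

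**Step 5. What the repaired set would deliver.** This assumes complete data and no baseline imbalance, with SD the residual standard deviation.
- Placebo pooled over three T2DM cohorts: SE = SD × √(1/9 + 1/9) = 0.471 SD; df = 36 − 4 − 1 = 31; 90% CI half-width ≈ 0.80 SD.
- One cohort with its own 3 placebo participants: SE = SD × √(1/9 + 1/3) = 0.667 SD; df = 12 − 2 − 1 = 9; half-width ≈ 1.22 SD.

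**Step 6. Is it cured elsewhere?** Nothing in either document adds placebo participants to the PD set or names another set for these contrasts. SAP 2.1 records only the removal of MDG and glucose AUC0-4. The version 2 change log lists no edit to Section 4.

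**The case against.** The strongest reply is that this is a drafting slip carried over from the PK sets and that nobody would be misled. SAP 5.2.3 to 5.2.5 ask for each treatment against placebo, and a run without placebo would fail at once. The study tests no hypotheses, no primary or secondary analysis is involved, and protocol 9.3.4 allows exploratory analyses to be left out of the CSR. All of that is right, and it limits the importance of the point. It does not make the text executable: the analyst must still override a written set definition.

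Four narrower points also deserve an answer:
- **The label exploratory is loose for one of the eight.** The 4-beta-hydroxycholesterol/cholesterol ratio sits among the SAP's other endpoints and is not in the visible objectives table. Protocol 9.3.4 makes its analysis conditional and keeps it out of the CSR. The count of eight stands as seven listed exploratory endpoints plus this ratio.
- **The 24 contrasts depend on the planned design.** A single T2DM cohort would give 8. If one of three cohorts were in obesity, the meal-test endpoints and HbA1c would drop out there, giving 8 + 8 + 4 = 20. The number estimable is 0 in every case.
- **The 25% is a planned proportion.** Cohort sizes are approximate, and participants who discontinue may be replaced.
- **A second repair exists.** The Full Analysis Set already includes placebo and could be named in SAP 6.4.1 to 6.4.4. That is another route to the same correction.

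**Conclusion.** The point holds. As written, the set excludes the entire comparator (9 of 36 planned participants), and none of the at least 24 placebo contrasts required under the planned design is estimable, across eight endpoints. That none is estimable follows from the set definition alone. Only the count of 24 rests on the assumptions in Step 3. A placebo-randomized participant given active drug in error would enter the set, but that does not supply a placebo arm.

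The effect is confined to endpoints that are neither primary nor secondary. It creates no bias. It leaves intact the active-arm means and summaries, the safety analyses (Safety Analysis Set) and the PK analyses. Body weight is also unaffected, since SAP 6.4 gives it neither a set nor a model. It should be fixed, because the stated set makes the stated analyses impossible.

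**What to change.** In SAP Section 4, define the PD set as randomized participants given one or more doses of study intervention, whether PF-07081532 or placebo, for whom at least one PD parameter is available. Add a line to SAP 2.1 recording the departure from protocol Table 4. Leave both PK sets as they are.

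Protocol Section 9 lets the SAP modify the protocol and calls for an amendment only for major changes to primary endpoint definitions or their analyses. None is needed here, and Table 4 can be aligned if the protocol is amended for another reason.

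The cost is one phrase and one line, with no new data or participants.

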5. GENERAL METHODOLOGY AND CONVENTIONS

5.1. Hypotheses and Decision Rules

Not applicable

5.2. General Methods

5.2.1. Analyses for Continuous Endpoints

Continuous endpoints and relevant safety endpoints will be presented using summary statistics: number of observations, arithmetic mean, standard deviation, median, minimum and maximum values.

